Rationale: Due to variability observed in previous batch strength, patients in Cohort 3 have received different doses when calculated by measured strength. While strength remained within specification, one patient has received 0.33×10^6 TU/eye dose, while the two following patients (treated with a new batch) received 2.4×10^6 TU/eye dose. Following DSMB review additional safety data in Part A was requested. Next two dose levels based on dilution from the measured batch strength will be investigated. This will provide additional safety information and improve dose selection for Parts B and C.
- Adding mention of a diluent for IMP
Rationale: dilution is needed to administer above mentioned additional dose levels.
- Inclusion criteria modified to better define target population
Rationale: Following new natural history data and DSMB recommendations, BCVA lowest threshold and minimal EZ zone area is added in order to select patients with some residual photoreceptor zone and some visual function, who could benefit more from treatment. ERG is removed from inclusion criteria since it does not appear to provide additional benefit for selection of the target population.
- Prophylactic glucocorticoid schedule added as mandatory after surgery and IMP injection
Rationale: anti-inflammatory regimen is added to decrease the risk of intraocular inflammation following the subretinal injection procedure. This modification is agreed with DSMB following two cases of uveitis classified as serious adverse events following subretinal injection of lentiviral vectors (one case in this study, the other with another project using the same lentiviral vector technology). The DSMB, in agreement with study Investigators, reviewed the cases and recommended the modification of the protocol with regard to glucocorticoids in order to reduce the occurrence of post-operative ocular inflammation.
- Additional list of ophthalmic AESIs added for better safety.
Rationale: additional list of ophthalmic AESIs will permit early reception of these safety events in sponsor's safety database, with more detailed data reported. This will ensure earlier monitoring for potential safety signals.
- Simplifying retinotomy description
Rationale: this will allow better adaptation of retinotomy and IMP injection to individual patients, with respect to lesion size and target retinal areas.
- Correction of baseline definition:

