4.4 SAR421869 DRUG DEVELOPMENT

SAR421869

The SAR421869 product and [REDACTED] is are both presented as a frozen liquid formulation that must be stored at $\leq -70^{\circ}\text{C}$.

The product is shown in [Table 1](#).

A target strength of 4.7×10^6 TU/mL will be produced which corresponds to undiluted material from the manufacturing process. Additional lower dosage strengths will be prepared from this material by dilution.

Table 1 - Components of the Medicinal Product

Product description	Quantity	Function	Reference to Standards
Active Substance: SAR421869	$\geq 6.0 \times 10^5$ to $< 1.5 \times 10^7$ TU/mL Target strength: 4.7×10^6 TU/mL	Active	
[REDACTED]	[REDACTED]	[REDACTED]	

Once SAR421869 is completely thawed, the appearance is a “turbid or clear colorless suspension free from particulates”. Upon thawing of [REDACTED] the appearance is a clear colorless solution, having no visible particulates. More detail information is provided in the study pharmacy manual.

Mechanism of Action

The protein encoded by the SAR421869 vector is the unmutated form of human myosin VIIa. Myosin VIIa protein has been localized to connecting cilium in photoreceptors and the apical processes of the RPE. Myosin VIIa protein is always co-localized with cilia, which indicates a role in maintaining axonemal structures or function. A defect in axonemal transport of rhodopsin has been suggested as a cause of RP. Consequently, mutations that affect the MYO7A gene can result in RP and vision loss. SAR421869 is a lentiviral vector product aimed at introducing normal MYO7A cDNA which codes for the relatively large functional myosin VIIa protein (2215 amino acids) in the RPE cells and photoreceptors, thereby restoring normal cellular function in both cell types and attenuating vision loss associated with Usher syndrome Type 1B.

Lentiviral vectors are advantageous for gene therapy applications for several reasons: they deliver genes stably and permanently into the genome of transduced cells *in vivo*, they are capable of transducing non-dividing cells and can carry large expression cassettes ([22](#)).

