It is anticipated that up to three additional patients may need to be enrolled during the study to replace those who fail to complete the first six months of follow-up appointments.

All patients will be followed for 48 weeks. After this period they will enter an open-label safety study for long-term follow-up. Patients will attend visits at a minimum interval of one visit every six months for assessments that will include ophthalmological examinations and recording of adverse events for 240 weeks (5 years).

In addition, the investigator will conduct visits/contact the patient by telephone for a subsequent 10 years at a minimum interval of once a year to monitor delayed adverse events.

The long-term follow-up of patients in the current study will be described in a separate protocol.

In the event that a patient dies during the study then consent for a post-mortem will be sought from the patient's family. In the event of development of an infection that is classified as an important medical event, particularly any opportunistic infection or onset of an autoimmune condition, effort will be made to collect data regarding the infectious agent and the outcome of the relevant investigations to characterize the autoimmune disease.

Table 3 - Study Design and Dosing Schedule

Part A

Cohort	Age (yr)	Number of patients	Subretinal Injection		
			Vector total dose per eye		
			by target strength (TU/eye)	by measured strength (TU/eye)**	Volume
1	≥18	3	1.4x10 ⁵	2.1x10 ⁴	300 µL
2	≥18	3	4.7x10 ⁵	1.1x10 ⁵	300 µL
3a	≥18	1	1.4x10 ⁶	0.33x10 ⁶	300 µL
3a	≥18	2	1.4x10 ⁶	2.4x10 ⁶	300 µL
3b	≥18	3	-	0.33x10 ⁶	300 µL
3c	≥18	3	-	1.4x10 ⁶	300 µL

Part B

Cohort	Age (yr)	Subretinal Injection		
		Number of patients	Vector total dose per eye	Volume
4	≥18	Up to 6	MTD	300 µL

Part C

Cohort	Age (yr)	Subretinal Injection		
		Number of patients	Vector total dose per eye	Volume
5	6-17	Up to 6	MTD	300 µL

Note: * dose as calculated from target product strength;

** dose as calculated from dilution (as applicable) of measured strength

Alternative Treatment following SAR421869 Administration

The re-administration of SAR421869 has not currently been assessed in nonclinical studies.

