13.4.2 Ophthalmological Safety Endpoints

Changes in other safety endpoints will be summarized at each visit; in addition, where appropriate, individual profile plots and mean plot of changes in the variable against time will be presented. The primary time points will be considered the 48-week (12-month) visit; the individual change at this time point only will be plotted against dose received.

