8.3.2 BCVA, Ocular Inflammation and IOP

Table 3L lists the primary outcomes of BCVA, ocular inflammation and IOP for the study and fellow eyes by patient and visit, Tables 3M and 3N summarize mean changes in BCVA and IOP, respectively, by cohort and visit for the study and fellow eyes and Table 3O summarizes the number and percentage of individuals with elevated (≥ 25 , ≥ 30 and ≥ 35 mmHg) IOP in the study eye. Changes in ophthalmic inflammation by dose group, visit and eye will also be summarized in Table 3P. Ophthalmic outcome data will be displayed graphically in plots similar to Figures 3Q and 3R. Tables and plots will be given for the study eye as well as for the fellow eye, and labeled appropriately.

Table 3L: Ophthalmic Outcome Listing for Study Eye and Fellow Eye by Patient and Visit

Patient ID	Visit	Study	IOP		BCVA		Anterior Cells		Anterior Flare		Vitreous Cells		Vitreous Haze		Macular Edema	
			Fellow	Study	Study	Fellow	Study	Fellow	Study	Fellow	Study	Fellow	Study	Fellow	Study	Fellow

Table 3M: Mean Changes from Pre-surgical BCVA by Cohort and Visit

Cohort	Visit	Study Eye					Fellow Eye				
		N	Mean	Std	Min	Max	N	Mean	Std	Min	Max

Table 3N: Mean Changes from Pre-surgical IOP by Cohort and Visit

[figure not shown]
Cohort	Visit	Study Eye					Fellow Eye				
		N	Mean	Std	Min	Max	N	Mean	Std	Min	Max

Table 3O: Patients Experiencing Elevated IOP in the Study Eye Following Treatment by Cohort

Cohort	IOP ≥ 25 mmHg				IOP ≥ 30 mmHg				IOP ≥ 35 mmHg			
	No		Yes		No		Yes		No		Yes	
	N	%	N	%	N	%	N	%	N	%	N	%
1												
2												
3												
4												
5												
All												

[figure not shown]
Table 3P: Changes in Ophthalmic Inflammation in the Study Eye by Cohort and Visit

Cohort	Visit	Anterior Chamber Cells		Anterior Chamber Flare		Vitreous Cells				Vitreous Haze			
		No Change	Half-Step Increase	No Change	1-Step Increase	Half-Step Decrease	No Change	Half-Step Increase	2-Step Decrease	1-Step Decrease	No Change	Half-Step Increase	
		N	%	N	%	N	%	N	%	N	%	N	%

Figure 3Q: Ophthalmic Outcomes Over Time (Days from Surgery) by Patient

Mean changes from Baseline (Day -28) will be plotted for ophthalmic outcomes versus dose cohort in a plot similar to Figure 3R.

Figure 3R: Mean Change in Ophthalmic Outcome from Baseline by Dose Cohort

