The purpose of this memorandum is to document that the Table of Contents for the final analysis for TDU13600 will differ from the Table of Contents in the currently approved version 2 of the SAP, dated 22JUL2016. The format of the tables will be the same as those in the SAP, except that the adverse event tables will be updated to the format used for the 23MAY2018 DSMB Report for SAR422459. The TOC and the adverse event table shells to be used for the final TLFs are included below.

Coordinating Center

Statistician Signature:

[figure not shown]
Date: 30AUG2019

Sponsor Statistician

Signature:

[figure not shown]
Date: 04SEP2019

Coordinating Center

Director Signature:

Date: 24SEP2019

TOC FOR ALL TLFs FOR TDU13600

- [Table 1A](#): Screening and Surgery Dates and Visit Completion by Cohort
- [Figure 1B](#): Patient Flow Diagram
- [Table 1C](#): Study Follow-up Completion and Withdrawal (including deaths)
- [Table 2A](#): Demographics Summary by Cohort
- [Listing 2B](#): Detailed Demographic Listing by Cohort
- [Listing 2C](#): General Medical History by Patient
- Listing 2D: Study Eye Ocular History by Patient
- Listing 2E: Fellow Eye Ocular History by Patient
- [Table 2F](#): Baseline Physical Examination Parameters by Cohort
- Table 2G: Reproductive Status by Patient
- Listing 2H: Detailed Surgery Listing by Patient
- Table 3A: Number and Percentage of Patients Experiencing TEAEs or No Events by Type of Event and Cohort
- Table 3B: Number of Patients Experiencing TEAEs by MedDRA SOC, HLGT, HLT, PT, and Cohort
- Table 3C: Number of Patients with TEAEs of Special Interest by MedDRA SOC, HLGT, HLT, PT, and Cohort
- Table 3D: Number of Patients with SAEs by MedDRA SOC, HLGT, HLT, PT, and Cohort
- Table 3E: Number of Patients Experiencing Inflammatory TEAEs by MedDRA SOC, HLGT, HLT, PT, and Cohort
- Table 3F: Number of Patients with TEAEs Related to IMP by MedDRA SOC, HLGT, HLT, PT, and Cohort
- Table 3G: Number of Patients with TEAEs Related to Procedure by MedDRA SOC, HLGT, HLT, PT, and Cohort
- [Table 3H](#): Listing of Adverse Events Prior to Treatment by Patient and Cohort
- [Table 3I](#): Listing of TEAEs by Patient and Cohort
- [Table 3J](#): Listing of Treatment Emergent Adverse Events of Special Interest by Patient and Cohort
- Table 3K: Listing of Treatment Emergent Serious Adverse Events by Patient and Cohort
- [Listing 3L](#): Ophthalmic Outcome Listing for Study Eye and Fellow Eye by Patient and Visit

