- [Table 3M](#): Mean Changes from Pre-surgical BCVA by Cohort and Visit
- [Table 3N](#): Mean Changes from Pre-surgical IOP by Cohort and Visit

- Table 3O: Patients Experiencing BCVA Change in the Study Eye at Week 48 Following Treatment by Cohort
- Table 3P: Patients Experiencing Elevated IOP in the Study Eye at Week 48 Following Treatment by Cohort
- **Tables 3Q-3S:** Changes in Ophthalmic Inflammation in the Study Eye by Cohort and Visit
- Figures 3T-3V: BCVA in Study and Fellow Eyes by Patient in Cohort X
- Figures 3W-3Y: IOP in Study and Fellow Eyes by Patient in Cohort X
- Figure 3Z: Mean Changes in BCVA in the Study Eye over Time by Cohort
- Figure 3AA: Mean Changes in IOP in the Study Eye over Time by Cohort
- **Listing 3BB:** Listing of Patients with Abnormal and/or Clinically Significant Labs
- Listing CC: Abnormal Physical Examination Listing by Patient
- **Table 3DD:** Mean Change in Continuous Laboratory Parameters by Cohort and Visit
- **Listing 3EE:** OCT Listing by Patient and Visit
- Figures 3FF-3HH: Central Retinal Thickness (OCT) for Study and Fellow Eyes in Cohort X
- Figures 3II-3KK: Macular Volume (OCT) for Study and Fellow Eyes in Cohort X
- Table 3LL: Change from Baseline in Vital Signs by Cohort and Visit
- **Listing 4A:** Static (GATE) Perimetry Data by Patient
- Figures 4B-4D: Volume of Full Field Hill of Vision Measured by Static (GATE) Perimetry by Patient in Cohort X
- Figures 4E-4G: 111pt grid-Volume of Full Field Hill of Vision Measured by Static (GATE) Perimetry by Patient in Cohort X
- **Listing 4H:** Kinetic (SKP) Perimetry Data by Patient
- Figures 4I-4K: SKP Data in Study Eyes by Patient in Cohort X
- **Listing 4L:** Full Field ERG Response (Study Eye) Amplitude and Implicit Time Data by Cohort, Patient and Visit
- **Table 4M:** Mean Peak Amplitudes and Latencies at Baseline (mfERG) by Cohort and Patient
- **Table 4N:** Central Field (Rings 1-3) Summary mfERG Data by Cohort and Patient
- **Table 4O:** Peripheral Field (Rings 4-6) Summary mfERG Data by Cohort and Patient
- Listing 5A: Detailed Listing of Immunologic Results from Blood Samples by Cohort and Patient
- Listing 5B: Biodistribution Endpoint Data

ADVERSE EVENT TABLE SHELL FOR TDU13600

PRIMARY SYSTEM ORGAN CLASS HLGT: High Level Group Term HLT: High Level Term Preferred Term n(%)	Cohort 1 (1.4×10^5 TU) (N=3)	Cohort 2 (4.7×10^5 TU) (N=3)	Cohort 3 (1.4×10^6 TU) (N=3)	All Cohorts (N=9)
Any Class	X (X%)	X (X%)	X (X%)	X (X%)
SOC1	X (X%)	X (X%)	X (X%)	X (X%)

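### The final adverse event tables label dose by unmarked target strength and pool a 7.3-fold measured-dose range in Cohort 3; the protocol's plot against dose received is missing from the output list

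*SAP*

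**What the plan says.** Protocol 4.4 sets a target strength of 4.7×10^6 TU/mL, "which corresponds to undiluted material from the manufacturing process", within a specification of at least 6.0×10^5 and below 1.5×10^7 TU/mL. Table 3 in Protocol 7 gives Part A doses in two columns, by target strength and by measured strength. A footnote defines the second as "dose as calculated from dilution (as applicable) of measured strength". Cohort 3a has one target dose, 1.4×10^6 TU/eye, but two measured doses. The Amendment 8 rationale explains why: the first patient had 0.33×10^6 TU/eye, while "the two following patients (treated with a new batch) received" 2.4×10^6 TU/eye.

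On analysis, Protocol 13.4.2 says of the ophthalmological safety endpoints that "the individual change at this time point only will be plotted against dose received", with Week 48 as the time point. Section 13.4.3 uses the same words for the secondary endpoints, with Weeks 24 and 48.

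SAP 3.0 lists target doses only. SAP 8.3.2 plans means by cohort rather than individual values: "Mean changes from Baseline (Day -28) will be plotted for ophthalmic outcomes versus dose cohort in a plot similar to Figure 3R". The August 2019 memo then replaces the SAP's list of outputs. It states that "The format of the tables will be the same as those in the SAP, except that the adverse event tables will be updated", following a May 2018 DSMB report for SAR422459. Its adverse event shell has columns at 1.4×10^5, 4.7×10^5 and 1.4×10^6 TU, the last headed "Cohort 3 (1.4×10^6 TU) (N=3"), and a total of nine patients. Its mean-change figures run over time, for example Figure 3Z, "Mean Changes in BCVA in the Study Eye over Time by Cohort".

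**The concern.** The primary objective is the safety of ascending doses, and the adverse event tables are where a reader links events to dose. The shell does not state the basis of its dose headings, although the protocol amended a year before carries two. The ambiguity is real: in Table 3 the figure 1.4×10^6 is both the target dose of Cohort 3a and the measured dose of Cohort 3c, and each has three patients.

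The documents themselves treat the measured-dose difference as relevant to safety. According to the Amendment 8 rationale, the DSMB asked for more Part A safety data after the Cohort 3 discrepancy, and the next dose levels were defined from measured strength. Pooling the three patients under one target figure hides that difference in the final tables. The protocol's individual plots against dose received would have shown it, and they are absent from the output list.

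**Working it through.** **Inputs.** Target strength and specification from Protocol 4.4; volume 300 µL and both sets of doses from Protocol 7, Table 3; column doses and patient numbers from the memo's shell.

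**Reproducing the heading.** 4.7×10^6 TU/mL × 0.3 mL = 1.41×10^6 TU, within 0.7% of the heading. The other two headings equal the target column for Cohorts 1 and 2. The total is 3 + 3 + 3 = 9. The headings are therefore target doses. With a total of nine and no 3b or 3c columns, Cohort 3 in the shell is taken to be Cohort 3a.

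**Heading against measured dose.**

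| Group | n | Heading (TU) | Measured (TU/eye) | Ratio |
|---|---|---|---|---|
| Cohort 1 | 3 | 1.4×10^5 | 2.1×10^4 | heading 6.67-fold higher |
| Cohort 2 | 3 | 4.7×10^5 | 1.1×10^5 | heading 4.27-fold higher |
| Cohort 3a, first patient | 1 | 1.4×10^6 | 0.33×10^6 | heading 4.24-fold higher |
| Cohort 3a, next two | 2 | 1.4×10^6 | 2.4×10^6 | heading 1.71-fold lower |

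So 3 + 3 + 1 = 7 patients were below their heading, two were above it, and none was at it.

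**Steps between adjacent measured levels.**
- 1.1×10^5 / 2.1×10^4 = 5.24
- 0.33×10^6 / 1.1×10^5 = 3.00
- 2.4×10^6 / 0.33×10^6 = 7.27 (7.0 to 7.5 allowing for rounding of the two doses)

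Four measured levels appear in three columns, and the largest step lies inside the Cohort 3 column. The 0.33×10^6 patient is closer to Cohort 2 (3.0-fold) than to the other two patients in the same column (7.3-fold).

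**Effect on a table entry (illustrations).**

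| Event occurs in | Pooled, under 1.4×10^6 | Split by measured dose |
|---|---|---|
| One patient at 2.4×10^6 | 1/3 (33%) | 0/1 at 0.33×10^6; 1/2 (50%) at 2.4×10^6 |
| Both patients at 2.4×10^6 | 2/3 (67%) | 0/1 at 0.33×10^6; 2/2 (100%) at 2.4×10^6 |
| Only the patient at 0.33×10^6 | 1/3 (33%) | 1/1 at 0.33×10^6; 0/2 at 2.4×10^6 |

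**What a target label can convey.** Undiluted product within specification gives from 6.0×10^5 × 0.3 = 1.8×10^5 to below 1.5×10^7 × 0.3 = 4.5×10^6 TU/eye, a 25-fold range. If Cohort 3a was given undiluted, as Protocol 4.11 indicates for the highest dose, the implied strengths are 0.33×10^6 / 0.3 = 1.1×10^6 and 2.4×10^6 / 0.3 = 8.0×10^6 TU/mL. Both are within specification, so meeting it does not identify the dose.

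**Other outputs.** The adverse event listing shells in SAP 8.3.1 carry cohort and surgery date but no dose. The patient profile in SAP section 9 records only whether the full dose was given. Listing 2H, the detailed surgery listing, has no shell. In the memo's list, the BCVA and IOP figures are by patient within a cohort or mean change over time by cohort. No title names a dose axis, and the SAP's Figure 3R has no counterpart there.

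**The case against.** The strongest reply is that the shell breaks no rule on adverse event tables. Protocol 13.4.1 does not ask for them by measured dose, SAP 7.3.1 summarises by dose cohort, and the headings are correct as target doses for product within specification. That stands: the fault is the unstated basis and the pooling, not a breach of 13.4.1.

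It can also be said that nine patients are few enough to read one by one, that profiles and listings exist for this, and that surgery dates with the Amendment 8 rationale would let someone rebuild the split. This is true, but it needs work outside the tables. It is also uncertain what the final listings will contain: the memo moves the adverse event tables to a format that is not reproduced in full, and Listing 2H might show dose. Neither possibility supplies a column label or the required plot.

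The MTD rests on DSMB judgement, and nothing shows this table feeding that decision. That limits the consequence to how results are reported and read. Columns of one and two patients are very small, though three is small already and a pooled column can stay.

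Finally, the protocol does not say whether dose received means target or measured dose. That affects the choice of axis, not the finding, because no plot on either scale is listed. Figures confined to one cohort could not show the relation with dose across cohorts.

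**Conclusion.** The concern holds and should be fixed. The shell's headings are target doses with no statement to that effect, and they differ from measured dose by 1.7- to 6.7-fold. Cohort 3 combines 0.33×10^6 (n=1) and 2.4×10^6 (n=2) TU/eye, a 7.3-fold spread. The plots of individual change against dose received, required in two sections of the protocol, are absent from the list of final outputs.

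This rests on two assumptions: that the shell's Cohort 3 is Cohort 3a, which the patient numbers strongly support, and that Table 3 records the measured doses correctly. The comparison does not say that either dose basis is wrong, only that the tables must state which one they use.

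**What to change.** 1. In the adverse event shell, give both target and measured dose in every column heading, each marked as such.
2. Split Cohort 3a into 0.33×10^6 (n=1) and 2.4×10^6 (n=2) TU/eye measured, with a pooled Cohort 3 column if wanted. Carry the split into the other tables by cohort, and add each patient's measured dose to the adverse event listings. Add columns for 3b and 3c only if those patients were dosed.
3. Restore the plots of individual change against dose received: Week 48 for ophthalmological safety endpoints, Weeks 24 and 48 for secondary endpoints. Use measured TU/eye, because on the target scale all three Cohort 3 patients share one position.
4. Reconcile the target-only dose levels in SAP 3.0 with the two-column Table 3 in Protocol 7, so that every reported dose level, including any MTD, states its basis.

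The cost is shell and memo wording, one patient-level dose variable that the protocol already tabulates by cohort, and plots it already requires. Conduct, dosing and data collection do not change. The drawback is columns of one and two patients, which should be read as counts rather than percentages.
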